### 9.4 *Statistical methods to be employed*

#### 9.4.1 **General Considerations**

All continuous study assessments will be summarized by treatment and time point (as applicable) using descriptive statistics (n, mean, median, standard deviation, minimum, and maximum). All categorical study assessments will be summarized by treatment and time point (as applicable) using frequency counts and percentages.

Hypothesis testing, unless otherwise indicated, will be performed at a two-sided 0.05 significance level. Where applicable, two-sided 95% confidence intervals will be reported. All p-values will be displayed to four decimal places, with p-values less than 0.0001 presented as '<0.0001' and p-values greater than 0.9999 presented as '>0.9999'. Difference between Articaïne Sterile Topical Ophthalmic Solution (AG-920) and Proparacaine will be calculated as Articaïne Sterile Topical Ophthalmic Solution – Proparacaine, with the 95% CI of the difference being reported for the reference of the treatment therapeutical equivalence.

All study data will be listed by treatment, subject, time point, and eye (as applicable).

Statistical methods will be more fully described in a separate document (Statistical Analysis Plan).

#### 9.4.2 **Interim analyses**

There is no planned interim analysis.

### 9.4.3 Analysis of Baseline Data

Demographic and baseline characteristics such as age, sex, ethnicity, race, and iris color will be summarized and listed. Depending upon the extent of medical and ocular history and concomitant medications in these healthy subjects, coding systems such as MedDRA and WHODrug will be used, and these data will be summarized and listed.

### 9.4.4 Subject Disposition

Subject enrollment and exit status (completed or discontinued) will be summarized and listed.

### 9.4.5 Protocol Deviations

Important protocol deviations are deviations from the protocol that potentially could have a meaningful impact on study conduct, or on the primary efficacy or key safety outcomes for an individual subject. The criteria for identifying important protocol deviations will be defined within the appropriate protocol-specific document. Important protocol deviations will be reviewed as part of the ongoing data cleaning process and all important deviations will be identified and documented prior to unmasking to confirm exclusion from analysis sets. Further details will be provided in the SAP.

### 9.4.6 Analysis of Efficacy

Analyses will be performed primarily on the ITT population and will be repeated on the PP population to determine robustness of results. For the primary efficacy endpoint of the proportion of subjects in whom there was adequate local anesthetic effect to perform an eye exam for which the subject is seeing the ophthalmologist, a Pearson chi-square test will be used for the comparison of the two proportions from the two treatment groups. In addition, a two-sided 95% confidence interval for the difference in response rates between the two treatment groups will be calculated. If the difference in response rates is around zero and the *P* value is NOT statistically significant (i.e.,  $P > 0.05$ ), then the therapeutical equivalence of AG-920 to the Proparacaine will be claimed, without reference to a pre-defined non-inferiority margin. The 95% CI of the difference in response rates will be reported to measure the extend or margin of the efficacy equivalence of AG920 to Proparacaine.

Sub-group analyses based upon pre-study characteristics such as sex, iris color, age, and race may be completed to further investigate the efficacy and safety measures.

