### 9.2 Sample Size Considerations

The sample size of approximately 70 subjects to be randomized in a 1:1 allocation ratio for AG-920 and reference groups is as directed by the U.S. FDA for a Pediatric Study Plan, rather than being estimated based on a pre-defined non-inferiority margin commonly used for the trial design of therapeutical equivalence. The Sponsor plans to enroll up to 70 subjects in order to obtain at least 60 evaluable subjects.

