### 9.4.8 Adverse Events

Verbatim descriptions of AEs will be mapped to MedDRA thesaurus terms and presented in a data listing. Treatment emergent AEs, those that occur after the first dose of study medication, will be summarized by treatment group using frequency counts and percentages for each System Organ Class (SOC) and Preferred Term (PT) within each SOC. Summaries will be presented separately for ocular and non-ocular AEs. These summaries will also be presented by the relationship to the

Investigational Medicinal Product (related, unrelated) and by severity of the AE (mild, moderate, severe). Fisher's exact test will be used to test the difference in proportions of subjects with each AE between treatment groups (SOC and PT).

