### 2.9.1 Primary efficacy analysis

The primary efficacy endpoint for this study is the proportion of subjects with anesthetic effect that is adequate for eye exam as assessed by the PI at 2-4 minutes post application of the dose. The definition of the primary efficacy endpoint is given in [Section 2.6.1](#). The non-parametric Cochran-Mantel-Haenszel (CMH) test with adjustment for study eye side will be used to examine the difference and/or therapeutic equivalence in proportion of subjects with anesthetic effect at 2-4 minutes post dose between the active treatment group and active-control group.

In primary efficacy analysis, rather than to reject the null hypothesis when there is a difference ( $P \leq 0.05$ ) between AG-920 and active-control treatments, this study is designed to accept the null hypothesis that there is no difference in anesthetic effect between AG-920 and active-control treatments ( $P > 0.05$ ), indicating the therapeutic equivalence of AG-920 to Proparacaine without reference to a pre-defined non-inferiority margin.

To further measure the therapeutical equivalence of anesthetic effect of AG-920 to the active-control treatment, between-group difference and its 95% confidence interval (CI) as well as its 90% CI in the proportion of subjects with anesthetic effect (yes=1) vs. non-effect (no=0) will be calculated using a two-way analysis of variance (ANOVA) model with treatment (the effect of interest) and study eye side as the effects. The study-eye-side effect is used as a blocking factor in the model to control the potential treatment differences among the study eye sides. The conventional 90% CI of the between-group difference will be used to measure the extent of the equivalent margin or non-inferiority margin of anesthetic effect of AG-920 to Proparacaine. The conventional rule of the 90% CI of the between-group difference lying

within +/-20% of the reference treatment will be employed to claim the therapeutic equivalence or non-inferiority of AG-920 to Proparacaine.

The primary efficacy analysis will be performed for the ITT population, which will include all randomized subjects who received the complete application of one study dose (i.e., two drops). The analysis model adjusts for the effect of the study eye side. The study-eye-side by treatment interaction will be examined through the summary descriptive statistics of subjects with anesthetic effect for each study eye side.

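### Protocol and SAP name different primary tests with no order of precedence; they can straddle 0.05, though rarely, and neither gives a P value if no child fails

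*Protocol*

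**What the plan says.** Protocol 9.4.6 makes the primary comparison unstratified: "a Pearson chi-square test will be used for the comparison of the two proportions from the two treatment groups". If the difference is near zero (no figure is given) and P exceeds 0.05, "then the therapeutical equivalence of AG-920 to the Proparacaine will be claimed, without reference to a pre-defined non-inferiority margin".

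SAP 2.9.1 names another test for the same endpoint and the same ITT population: "The non-parametric Cochran-Mantel-Haenszel (CMH) test with adjustment for study eye side will be used to examine the difference". It too reads P > 0.05 as equivalence: "this study is designed to accept the null hypothesis that there is no difference in anesthetic effect between AG-920 and active-control treatments". It then adds a rule that the protocol lacks. A 90% CI for the difference, from a two-way ANOVA on the yes/no outcome, lying "within +/-20% of the reference treatment will be employed to claim the therapeutic equivalence or non-inferiority of AG-920 to Proparacaine".

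The significance level is common ground (Protocol 9.4.1): "Hypothesis testing, unless otherwise indicated, will be performed at a two-sided 0.05 significance level". On size, Protocol 9.2 states: "The Sponsor plans to enroll up to 70 subjects in order to obtain at least 60 evaluable subjects". The visible text of neither document gives an expected success rate or a fallback for few or no failures on the primary endpoint.

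**The concern.** Both documents attach a conclusion to the side of 0.05 on which P falls, so the choice of test is part of the decision rule. With two tests named and no order of precedence, the rule is not fully fixed before the data are seen.

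The endpoint may also produce few failures, since only children judged capable of an eye exam are enrolled. At an assumed success rate of 90% to 98% and 30 to 35 per arm, expected failures run from 30 × 0.02 = 0.6 to 35 × 0.10 = 3.5 per arm. If there are none at all, a rule that requires P > 0.05 has nothing to work on.

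**Working it through.** **Inputs.** From the documents: 70 randomized 1:1 (35 per arm) or 60 evaluable (30 per arm), two-sided 0.05, and eye side right (OD) or left (OS) as the CMH stratum. Assumed: success rates and eye-side splits. The plan states no power or response rate, so it has no figure of its own to reproduce here.

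**Formulas** (no continuity correction). With a, b the successes and failures on AG-920, c, d those on Proparacaine, r the arm sizes and k the outcome totals:
- Pearson X² = N(ad − bc)² / (r₁r₂k₁k₂).
- CMH = [Σ(a − E)]² / ΣV over the two strata, with E = n₁m/N and V = n₁n₂m(N − m) / [N²(N − 1)], where m is the stratum's successes.

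**Example 1: AG-920 29/35, Proparacaine 34/35.**
- Pearson: 70 × (29×1 − 6×34)² / (35×35×63×7) = 2,143,750 / 540,225 = 3.968, P = 0.046.
- CMH, one eye 14/18 vs 16/17: a − E = 14 − 15.429 = −1.429, V = 1.102. Other eye 15/17 vs 18/18: a − E = 15 − 16.029 = −1.029, V = 0.485. Then 2.457² / 1.587 = 3.80, P = 0.051.
- SAP ANOVA 90% CI: −25.8 to −2.3 points.

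**Example 2: AG-920 27/30, Proparacaine 30/30, eye side unbalanced.**
- Pearson: 60 × (27×0 − 3×30)² / (30×30×57×3) = 486,000 / 153,900 = 3.158, P = 0.076.
- CMH, OD 17/17 vs 13/13: contributes 0 to both sums. OS 10/13 vs 17/17: a − E = 10 − 11.7 = −1.7, V = 0.686. Then 2.89 / 0.686 = 4.21, P = 0.040.
- SAP ANOVA 90% CI: −20.7 to −2.4 points.

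**What each rule returns**

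| | Protocol (Pearson) | SAP P rule (CMH) | SAP ±20% rule |
|---|---|---|---|
| Example 1 | no claim | equivalence | fails |
| Example 2 | claim, if −10 points counts as near zero | no claim | fails |

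The last column reads ±20% as percentage points. Read as 20% of the reference rate, it is 0.20 × 97.1 = 19.4 points in example 1 and 20 points in example 2, with the same result.

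**How often the tests disagree.** In 20,000 simulated trials per scenario, 35 per arm and random eye side: about 0.9% at 95/95, 3.3% at 75/95 and 4.2% at 80/95. Enumerating all tables at 30 per arm, an eye-side split of 17/13 against 13/17 gives 40 disagreeing tables with overall success of at least 85%. An exact 15/15 split in each arm gives none.

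**No failures.** Pearson's failure total is 0 and every V is 0, so both statistics are 0/0. The probability is p^N:

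| Assumed common rate | N = 60 | N = 70 |
|---|---|---|
| 95% | 4.6% | 2.8% |
| 98% | 29.8% | 24.3% |
| 99% | 54.7% | 49.5% |

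Every ANOVA residual is then 0, so its interval is 0 to 0 and meets ±20% with zero estimated variance.

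An unstratified Miettinen-Nurminen interval still has width in that case. At a true difference of −δ the constrained rates are 1 − δ and 1, so the limit solves δ/(1 − δ) = z²N / [n(N − 1)]. For 35/35 vs 35/35 at 95%: 3.841 × 70 / (35 × 69) = 0.1113, so δ = 0.1113/1.1113 = 0.100. The limits are about ±10 points.

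**The case against.** Four points on the other side carry weight.

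- **The SAP does not rest on P alone.** A reader might infer that an analyst could reach either trial conclusion from the same data by choosing the test. The examples do not support that. In example 1 the protocol and the SAP margin rule both refuse the claim. In example 2 the margin rule refuses it under either test, and the protocol would allow it only if −10 points counts as near zero, which it leaves undefined. This objection stands.
- **Disagreement is rare.** At high success rates it needs eye side to be unbalanced between arms. Whether the randomization list prevents that cannot be checked, because part of SAP 2.4 is redacted. This stands as well.
- **No failures need not be likely.** A reader might expect it in healthy children who can already undergo an eye exam, but the documents give no response rate and the chance is small at 95%. SAP 2.8 also counts a missing assessment as no effect, so the case needs complete ITT outcomes too.
- **The SAP may be meant to govern.** Protocol 9.4.1 leaves the fuller description of methods to the SAP, and 9.6 requires deviations from the statistical plan to be justified. That limits silent switching. It does not say that one named test replaces another, and the visible SAP text neither mentions the change nor explains it.

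A further tempting step is to treat the protocol's exact test for adverse events ("Fisher's exact test will be used to test the difference in proportions of subjects with each AE between treatment groups") as showing that the primary test is wrong. Neither document names an exact test for efficacy. Preferring one is a choice of method, not a contradiction in the plan.

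**Conclusion.** The concern holds in limited form and should be fixed. Two primary tests are prespecified for one endpoint and one population, with no statement of which governs. They can give P values on opposite sides of 0.05, in either direction. The frequency is about 0.9% of trials at an assumed 95% in both arms and 3-4% when true rates differ by 15-20 points.

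The mismatch adds to a conflict inside the SAP. In example 1 its P rule indicates equivalence while its margin rule does not.

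The zero-failure gap is certain in form but unknown in probability: 2.8%, 24% or 49% with 70 children at assumed common rates of 95%, 98% or 99%. In that case the protocol's rule returns nothing, and the SAP's interval passes without reflecting any sampling uncertainty.

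**What to change.** Before unmasking, write the same single primary method into Protocol 9.4.6 and SAP 2.9.1. Base the conclusion on a score-type confidence interval for the difference in success rates, such as Miettinen-Nurminen, stratified by eye side if that adjustment is kept. It replaces the ANOVA interval. State the criterion identically in both documents, including whether ±20% means percentage points or a fraction of the reference rate.

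Add one sentence for zero failures: no P value is quoted and the conclusion rests on the interval (95% limits about ±10 points at 35/35 vs 35/35). This sentence is needed because the score test of zero difference is also 0/0 there, so only the interval helps. The score method is itself a large-sample method, so it does not remove the small-count approximation.

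The cost is matching wording in two documents and a procedure option in the analysis program. The downside is a slightly wider interval and a less familiar method.

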### 9.4.7 Analysis of Safety

External eye exam measures and slit lamp biomicroscopy (if applicable) will be summarized at each measured time point using discrete summary statistics.

Visual Acuity data will be summarized at each time point organized by the age and clinically appropriate test, which may be continuous, categorical or both.

### 9.4.8 Adverse Events

Verbatim descriptions of AEs will be mapped to MedDRA thesaurus terms and presented in a data listing. Treatment emergent AEs, those that occur after the first dose of study medication, will be summarized by treatment group using frequency counts and percentages for each System Organ Class (SOC) and Preferred Term (PT) within each SOC. Summaries will be presented separately for ocular and non-ocular AEs. These summaries will also be presented by the relationship to the

Investigational Medicinal Product (related, unrelated) and by severity of the AE (mild, moderate, severe). Fisher's exact test will be used to test the difference in proportions of subjects with each AE between treatment groups (SOC and PT).

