## Summary

Study Number	AG-920-CS304	
Clinical Phase:	Phase 3	
Type of study	Efficacy and Safety	
Name of Investigational product:	Articaine Sterile Topical Ophthalmic Solution (AG-920)	
Name of Comparator product	0.5% Proparacaine Hydrochloride	
Duration of treatment per subject	1 day	
Objectives and Endpoints:	Primary Objective	Primary Endpoints
	To evaluate anesthetic efficacy of AG-920	The proportion of subjects in which an eye exam was able to be performed
	Secondary Objective	Secondary Endpoints
	To evaluate the safety and tolerability of AG-920	Incidence of AEs, TEAEs, SAEs, withdrawals due to TEAEs
Subject Population:	Healthy pediatric volunteers Exclusion criteria may be found in Section 4.2.	
Design:	Randomized, active-controlled, single-masked, parallel-group.	
Visit Schedule:	Study visits will consist of a Screening Visit, a dosing and eye exam visit, and a follow-up phone call	
Number of Investigational Sites:	1-3 US sites	
Estimated Total Sample Size:	Enroll up to 70 subjects to result in 60 evaluable subjects; ~30 per treatment group	
Plan for Data Analysis:	The sample size is as directed by the U.S. FDA for a Pediatric Study Plan.	
Investigational/Comparator Product(s), Dose and Mode of Administration	Subjects will receive a single dose (two drops) of IMP in one (study) eye. The IMP will be randomized as either AG-920 or Proparacaine HCl Ophthalmic Solution. The study eye will be randomized as either right eye (OD) or left eye (OS). The single dose will be administered by the clinic staff.	

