### 1.2 *Potential Risks and benefits to human subjects*

Minimal risks are expected with AG-920. Based upon clinical trials conducted to date, expected risks for subjects may include temporary, mild conjunctival/ocular hyperemia, eye pain, instillation site reaction (stinging/burning), and conjunctival hemorrhage upon instillation of the investigational medicinal product (IMP). For any additional information on AG-920 use, please refer to the [Investigator's Brochure](#).

Minimal risks are expected with the comparator, Proparacaine HCl ophthalmic solution. Occasional temporary stinging, burning and conjunctival redness may occur with the use of Proparacaine. A rare, severe, immediate-type, apparently hyperallergic corneal reaction (characterized by acute, intense and diffuse epithelial keratitis, a gray, ground glass appearance, sloughing of large areas of necrotic epithelium, corneal filaments and, sometimes, iritis with descemetitis) has been reported. Allergic contact dermatitis from Proparacaine with drying and fissuring of the fingertips has also been reported. For any additional information on Proparacaine use, please refer to the [Package Insert](#).

As this study is to be conducted in healthy pediatric subjects, there is no anticipated benefit other than the possibility that a subject's participation in the present study may help others in the future to have more options for local anesthesia before ophthalmic procedures.

Any new, unexpected adverse events (AEs) present among subjects in this clinical trial will be communicated to Investigators and to ethics committees or Institutional Review Board (IRBs) in accordance with local regulations.

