#### Adverse Events

Adverse events will be coded for preferred terminologies using Medical Dictionary for Regulatory Activities (MedDRA). AEs will be grouped into pre-treatment AEs, treatment-emergent AEs, and post-treatment AEs and will be reported separately, based upon the start date and time of the events compared to the start date and time of the treatment.

Adverse events will be defined as pre-treatment AEs if they occur prior to the treatment start date and time; as treatment-emergent AEs if they occur on or after the treatment start date and time and before the next day; and as post-treatment AEs if they occur after the treatment date.

Frequency of treatment-emergent AEs will be calculated for each body system, by preferred terminology, by treatment group, for number of subjects and percentage reporting the event.

The severity of the adverse events and the relationship to the investigational product will be summarized for each body system and preferred terminology by treatment group. Withdrawals due to adverse events will be summarized for each body system and preferred terminology by treatment group and will be listed with demographic variables for individual subjects.

Serious adverse events (SAE) (including deaths) will be listed for individual events.

Narratives will be provided for all deaths, non-fatal serious adverse events, and subjects withdrawn due to adverse events.

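### Adverse events are compared only by per-term Fisher tests in the protocol and not tested in the SAP, and neither document specifies an estimate or interval for the excess risk

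*Protocol*

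**What the plan says.** Protocol section 2 makes safety and tolerability the secondary objective. Its endpoints are the incidence of AEs, TEAEs and SAEs, and withdrawals due to TEAEs.

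Protocol 9.4.8 provides a descriptive summary (TEAEs "will be summarized by treatment group using frequency counts and percentages for each System Organ Class (SOC) and Preferred Term (PT") and one inferential step: "Fisher's exact test will be used to test the difference in proportions of subjects with each AE between treatment groups (SOC and PT". Protocol 9.4.1 sets the level: "Hypothesis testing, unless otherwise indicated, will be performed at a two-sided 0.05 significance level".

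On intervals, Protocol 9.4.1 has a general line, "Where applicable, two-sided 95% confidence intervals will be reported". It also describes an interval for AG-920 minus Proparacaine, but ties it to efficacy: "with the 95% CI of the difference being reported for the reference of the treatment therapeutical equivalence". Neither line is assigned to adverse events.

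SAP 2.9.3 says: "Frequency of treatment-emergent AEs will be calculated for each body system, by preferred terminology, by treatment group". SAP 5.3 lists the tables. Neither section names a Fisher test or an interval for adverse events. SAP 3.1 nevertheless says that the safety population serves comparative safety analyses. SAP 2.9.3 does test other safety data between arms, by chi-square for visual acuity and external eye exam abnormalities and by ANOVA for the slit-lamp score.

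The size is given in the Protocol Summary: "Enroll up to 70 subjects to result in 60 evaluable subjects; ~30 per treatment group".

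**The concern.** The protocol and the SAP do not describe the same analysis of the secondary endpoint. If the protocol governs, the reader gets one P value per SOC and per PT from small arms. If the SAP governs, the reader gets two columns of percentages and no stated comparison. In neither case do the documents commit to the figure a safety reader needs, which is the estimated excess on AG-920 and its upper limit.

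This matters because the subjects are healthy children with no anticipated personal benefit (Protocol 1.2), and the arms are too small for a non-significant term-level test to say much about a moderate excess. The reactions expected with AG-920 are known in advance ("temporary, mild conjunctival/ocular hyperemia, eye pain, instillation site reaction (stinging/burning), and conjunctival hemorrhage upon instillation"), so a grouped comparison can be fixed before the data are seen.

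**Working it through.** **Inputs from the documents.** Up to 70 children enrolled and 1:1 allocation give 35 per arm if all are dosed; 60 evaluable give 30 per arm. The test is Fisher's exact, two-sided 0.05. The plan gives no power, adverse-event rate or harm margin, so there is no figure of its own to reproduce.

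**Assumed inputs.** Proparacaine rates of 0 to 20%, with AG-920 rates above them.

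**Step 1: what a term needs to reach significance.** At 30 or 35 per arm, Fisher gives P ≤ 0.05 only from 6 events against 0, 8 against 1, or 9 against 2. Five against 0 gives P = 0.052 at 30 per arm and P = 0.054 at 35.

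**Step 2: miss rate.** Miss rate = 1 − Σ Bin(a; n, p_AG) × Bin(b; n, p_P), summed over all tables with P ≤ 0.05. When the Proparacaine rate is 0%, this reduces to the chance of at most 5 AG-920 events. For 0% versus 10% that is P(X ≤ 5), with X ~ Bin(30, 0.10) = 0.927 or X ~ Bin(35, 0.10) = 0.868.

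| Proparacaine vs AG-920 (assumed) | Excess, points | Missed, 35 per arm | Missed, 30 per arm |
|---|---|---|---|
| 0% vs 10% | 10 | 87% | 93% |
| 5% vs 15% | 10 | 86% | 91% |
| 5% vs 20% | 15 | 67% | 76% |
| 10% vs 30% | 20 | 55% | 63% |
| 20% vs 40% | 20 | 64% | 70% |
| 0% vs 25% | 25 | 10% | 20% |
| 5% vs 35% | 30 | 13% | 21% |
| 10% vs 45% | 35 | 11% | 17% |
| 20% vs 50% | 30 | 31% | 40% |

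Power is low for excesses of 10 to 20 points. At Proparacaine rates of 0 to 5%, excesses of 25 to 30 points are missed in only about 10 to 21% of trials. At higher Proparacaine rates the excess must be larger.

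**Step 3: what an interval adds.** Miettinen-Nurminen 95% intervals for AG-920 minus Proparacaine at 35 per arm:

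- 8 vs 3 events: Fisher P = 0.19; interval −3 to +32 points.
- 5 vs 0 events: Fisher P = 0.054; interval +3.6 to +29.5 points. Part of this contrast is Fisher's conservatism.
- 0 vs 0 events: Fisher P = 1; interval about −10 to +10 points. By hand, the limit is k/(1 + k) with k = 3.84 × (70/69)/35 = 0.111, which gives 0.100.

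For a single arm with no events, the exact one-sided 95% upper limit is 1 − 0.05^(1/n): 8.2% at 35 and 9.5% at 30.

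**Step 4: does pooling terms help?** Suppose four local-reaction terms each occur at 3% versus 12%. Each is missed about 89% of the time at 35 per arm.

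- If the terms are independent within children, the pooled rates are 1 − 0.97^4 = 11.5% and 1 − 0.88^4 = 40.0%. The pooled test misses 28% at 35 per arm and 36% at 30. The fair comparison is the chance that all four separate tests miss, 0.895^4 = 64% at 35 per arm.
- If the same children report all four terms, the pooled rates stay at 3% and 12% and nothing is gained.

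**The case against.** A reader might infer that a non-significant P value is all the safety comparison can show. The documents do not support that. Both report counts and percentages by arm, from which anyone can compute an interval. The protocol also breaks AEs down by ocular and non-ocular origin, relatedness and severity. The SAP adds study-eye and fellow-eye tables and tests on visual acuity, external eye exam and slit-lamp findings. If the SAP governs, there is no adverse-event P value to misread.

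A reader might also infer that the plan would accept P > 0.05 as proof of similar safety, because Protocol 9.1 and 9.4.6 and SAP 2.9.1 reason that way for efficacy. No passage extends that rule to adverse events.

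Nor can it be said that the tests miss most relevant harms. The documents give no rates and no harm threshold, and large excesses would usually be seen. The splitting argument is limited too, because Fisher is applied to SOCs as well as PTs and so already pools within an SOC.

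Finally, descriptive adverse-event tables are a workable choice for about 60 children at a size the protocol attributes to the regulator. All of this stands and limits the point. It does not remove the disagreement between the documents or supply the missing estimate.

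**Conclusion.** The point holds for adverse-event inference only. The protocol's single comparative method is a Fisher test per SOC and PT, the SAP omits it without replacement, and neither specifies an estimate or interval for excess adverse-event risk. The general interval wording in Protocol 9.4.1 is not tied to AEs.

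Under the assumed rates, a 10-point excess from a Proparacaine rate of 0 to 5% is missed about 86 to 93% of the time, and 5% versus 20% is missed 67 to 76%. The size depends on those assumptions, and the gain from pooling depends on how far terms overlap within children. This is a cheap improvement the sponsor should make; it does not mean that the trial reports no usable safety data.

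**What to change.** Reconcile Protocol 9.4.8 with SAP 2.9.3 and 5.3, and put the same text in both:

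- Report the risk difference (AG-920 minus Proparacaine) with a two-sided 95% Miettinen-Nurminen score interval for (a) any TEAE, (b) any study-eye TEAE and (c) a pooled group of expected local reactions.
- Define group (c) by a list of terms fixed before database lock. It should cover the reactions that Protocol 1.2 lists for both products, so that it does not lean towards one arm.
- Give exact 95% upper limits per arm for SAEs and for withdrawals due to TEAEs.
- Keep the SOC and PT tables descriptive, and label any P values there as descriptive.
- State that no claim of similar safety rests on P > 0.05.

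The TEAE window must be settled at the same time, since it decides which events are counted. Protocol 8.3 runs it to the follow-up call, while SAP 2.9.3 ends it on the dosing day.

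The cost is wording plus an added column in tables already planned (SAP Tables 4.1.2, 4.2.2 and 4.2.5) and one short pooled summary. No new data or subjects are needed. The downside is that the intervals will be wide, as the result for no events in either arm shows.
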